### **8.1.14 Study Medication Diary**

For participants who are discharged prior to receiving all 10 doses of study intervention, a paper Study Medication Diary and instructions on how to take study intervention will be provided for documentation of doses and assessment of compliance. Participants should complete the Study Medication Diary for each dose taken. In the event that the participant is (in the judgment of the investigator) unable to complete the diary, information regarding study intervention administration may be recorded by an LAR or other close contact who witnesses administration of the study intervention.

The Study Medication Diary will be reviewed in conjunction with capsule counts by study staff. The participant's Study Medication Diary doses will be recorded in the eCRF for all doses after discharge. The Study Medication Diary should be reviewed in conjunction with capsule counts by study staff with the participant to ensure compliance with completion and consistency with capsule counts. Capsule counts will be performed by study staff (expected versus actual) for each study intervention bottle according to the pharmacy manual.

The Study Medication Diary will be collected as soon as possible after the last dose (ie, 10th dose) of study intervention. If the EOT visit is performed prior to the last dose of study intervention, the Study Medication Diary should be collected no later than the Day 10 visit. The study intervention data as recorded in the participant's Study Medication Diary will be entered in the eCRF.

## **8.2 Efficacy Assessments**

### **8.2.1 Nasopharyngeal and Oropharyngeal Swabs**

NP and OP swabs will be collected at various timepoints as outlined in the SoA (Section 1.3) for qualitative and quantitative SARS-CoV-2 RT-PCR testing and SARS-CoV-2 genome sequencing. At study entry (Day 1), the samples should be collected prior to the first dose of study intervention. Additional information, including instructions for swab collection, storage, and shipping, can be found in the laboratory manual.

NP and OP swab collection may be adapted to remove 1 method or timepoints throughout the life of the study; this will be communicated via Protocol Clarification Letters.

### **8.2.2 Assessment of COVID-19 Signs, Symptoms, and Functional Status**

The investigator or medically qualified designee (consistent with local requirements) will assess COVID-19 signs and symptoms daily while the participant is hospitalized. After participant discharge, signs and symptoms will only be assessed on study visit days. Functional status will only be assessed at Day 1, Day 3, EOT, Day 10, Day 15, and Day 29.

The participant's ability to independently perform daily activities with minimal or no symptoms will be assessed and evaluated at the discretion of the investigator/designee.

### **8.2.3 Assessment of Level of Consciousness**

Level of consciousness will be assessed using the Alert, Voice, Pain, Unresponsive scale [Royal College of Physicians 2012]. This assessment is conducted in sequence and only 1 outcome should be recorded as follows:

- Alert: participant is fully awake
- Voice: participant responds (in any manner) when spoken to
- Pain: participant responds to painful stimulus
- Unresponsive: participant does not respond to voice or pain

### **8.2.4 Respiratory/Oxygenation Status**

SpO2 will be measured once daily via pulse oximetry (SoA, Section 1.3) after the participant has been at rest for at least 5 minutes. If applicable, FiO2 and arterial blood gas PaO2 should be reported. The oxygenation saturation level should be reported at a consistent time of day at each visit as noted in the SoA. Ensure the value is not impacted by external forces (eg, during rotating the participant's position).

Use of supplemental oxygen, including type (eg, oxygen from a conventional regulator or high flow heated and humidified device, non-invasive mechanical ventilation, invasive mechanical ventilation, ECMO) and flow rate (L/min) will be recorded on the appropriate eCRF. Supplemental oxygen requirements pre-morbid/pre-COVID-19 and between the onset of COVID-19 signs and symptoms and study randomization will be recorded (Section 8.1.4).

Note: Respiratory/Oxygenation Status collection at the LFU visit will be limited. As LFU will be a virtual visit, SpO2 will not be measured. Use of supplemental oxygen will be collected.

### **8.2.5 Hospitalization Status**

Hospitalization status will be assessed daily while hospitalized as outlined in the SoA (Section 1.3). The date and time that the participant is deemed medically ready for discharge will be recorded in addition to the actual date and time of discharge as applicable.

In the event of hospital discharge, the residence to which the participant was discharged and whether it was the residence occupied at the time of onset of COVID-19 symptoms will be ascertained.

In the event of re-hospitalization after initial discharge, hospitalization is defined as  $\geq 24$  hours of acute care in a hospital or similar acute care facility, including emergency rooms or facilities created to address hospitalization needs during the COVID-19 pandemic.

Information related to the re-hospitalization will be collected, including if the admission is related to COVID-19.

The Sponsor must be notified within 24 hours of site's awareness of a participant's hospitalization.

### **8.2.6 Survival Status**

Survival status (ie, whether the participant is alive or dead) will be assessed per the SoA (Section 1.3).

Site personnel should attempt to obtain information regarding vital status (including date last known to be alive, hospitalization, date of death, primary cause of death, and COVID-19 contribution to death) from the participant or other sources (eg, family members, other designated secondary contacts, hospital the participant stated they would most likely go to, clinic/hospital/medical records, and local or national databases), per the SoA (Section 1.3).

Information about death should be entered in the eCRF within 24 hours of a site becoming aware of a death.

## **8.3 Safety Assessments**

Details regarding specific safety procedures/assessments to be performed in this study are provided. The total amount of blood to be drawn over the course of the study (from pre-study to post-study visits), including approximate blood volumes drawn by visit and by sample type per participant, can be found in Appendix 2, [Table 11](#).

Planned time points for all safety assessments are provided in the SoA.

### **8.3.1 Physical Examinations**

A complete physical examination will be conducted at the screening visit by a nurse or other qualified healthcare provider. Height and weight will also be collected and recorded. A nurse or other qualified healthcare provider will also conduct directed physical examinations targeted at the participant's symptoms/complaints at all other in-person visits (in-clinic or at-home). Details of the physical examinations will be provided to an investigator or medically qualified designee (consistent with local requirements) for review and assessment per institutional standard.

### **8.3.2 Vital Signs**

Body temperature, heart rate, respiratory rate, and blood pressure will be assessed.

Blood pressure and heart rate measurements should be preceded by at least 5 minutes of rest for the participant in a quiet setting without distractions.

### **8.3.3 Electrocardiograms**

A local 12-lead ECG will be obtained and reviewed by an investigator or medically qualified designee (consistent with local requirements) as outlined in the SoA (Section 1.3). Calculation of heart rate and measurement of PR, QRS, QT, and QTc intervals may be manually calculated by a qualified physician or via an ECG machine that automatically calculates the values. Clinically significant findings must be documented in the source documents and captured in the appropriate eCRF.

If an ECG is performed for any medical reason while the participant is on study intervention or during the follow-up period, any clinically significant changes compared with the baseline ECG must be captured as AEs.

### **8.3.4 Clinical Safety Laboratory Assessments**

Refer to Appendix 2 for the list of clinical laboratory tests to be performed and to the SoA for the timing and frequency.

- The investigator or medically qualified designee (consistent with local requirements) must review the laboratory report, document this review, and record any clinically relevant changes occurring during the study in the AE section of the CRF. The laboratory reports must be filed with the source documents. Clinically significant abnormal laboratory findings are those which are not associated with the underlying disease, unless judged by the investigator to be more severe than expected for the participant's condition.
- All protocol-required laboratory assessments, as defined in Appendix 2, must be conducted in accordance with the laboratory manual and the SoA.
- If laboratory values from nonprotocol-specified laboratory assessments performed at the institution's local laboratory require a change in study participant management or are considered clinically significant by the investigator (eg, SAE or AE), then the results must be recorded in the appropriate CRF (eg, SLAB).
- For any laboratory tests with values considered clinically significantly abnormal during participation in the study or within 14 days after the last dose of study intervention, every attempt should be made to perform repeat assessments until the values return to normal or baseline or if a new baseline is established as determined by the investigator.

### **8.3.5      Pregnancy Testing**

- Pregnancy testing:
  - Pregnancy testing requirements for study inclusion are described in Section 5.1.
  - Pregnancy testing (serum) should be conducted at screening and on Day 29, approximately 24 days after the last dose of study intervention.
  - Additional serum or urine pregnancy tests may be performed, as determined necessary by the investigator or required by local regulation, to establish the absence of pregnancy at any time during the subject's participation in the study.

### **8.4      Adverse Events, Serious Adverse Events, and Other Reportable Safety Events**

The definitions of an AE or SAE, as well as the method of recording, evaluating, and assessing causality of AE and SAE and the procedures for completing and transmitting AE, SAE, and other reportable safety event reports can be found in Appendix 3.

Adverse events, SAEs, and other reportable safety events will be reported by the participant (or, when appropriate, by a caregiver, surrogate, or the participant's legally authorized representative).

The investigator and any designees are responsible for detecting, documenting, and reporting events that meet the definition of an AE or SAE as well as other reportable safety events. Investigators remain responsible for following up AEs, SAEs, and other reportable safety events for outcome according to Section 8.4.3.

The investigator, who is a qualified physician, will assess events that meet the definition of an AE or SAE as well as other reportable safety events with respect to seriousness, intensity/toxicity and causality.

#### **8.4.1      Time Period and Frequency for Collecting AE, SAE, and Other Reportable Safety Event Information**

All AEs, SAEs, and other reportable safety events that occur after the participant provides documented informed consent but before intervention randomization must be reported by the investigator if the participant is receiving placebo run-in or other run-in treatment, if the event causes the participant to be excluded from the study, or is the result of a protocol-specified intervention, including but not limited to washout or discontinuation of usual therapy, diet, or a procedure.

From the time of intervention randomization through 14 days following cessation of treatment, all AEs, SAEs, and other reportable safety events must be reported by the investigator.

Additionally, any SAE brought to the attention of an investigator at any time outside of the time period specified in the previous paragraph must be reported immediately to the Sponsor if the event is considered related to study intervention.

Additionally, all pregnancies with a conception date occurring within 28 days after the first dose of study intervention for female participants or within 90 days after the last dose of study intervention for female partners of male participants must be reported by the investigator.

Investigators are not obligated to actively seek AEs or SAEs or other reportable safety events in former study participants. However, if the investigator learns of any SAE, including a death, at any time after a participant has been discharged from the study, and he/she considers the event to be reasonably related to the study intervention or study participation, the investigator must promptly notify the Sponsor.

All initial and follow-up AEs, SAEs, and other reportable safety events will be recorded and reported to the Sponsor or designee within the time frames as indicated in [Table 3](#).

Table 3 Reporting Time Periods and Time Frames for Adverse Events and Other Reportable Safety Events

Type of Event	Reporting Time Period: Consent to Randomization/Allocation	Reporting Time Period: Randomization/Allocation through Protocol-specified Follow-up Period	Reporting Time Period: After the Protocol-specified Follow-up Period	Time Frame to Report Event and Follow-up Information to Sponsor:
NSAE	Report if: - due to protocol-specified intervention - causes exclusion - participant is receiving placebo run-in or other run-in treatment	Report all	Not required	Per data entry guidelines
SAE	Report if: - due to protocol-specified intervention - causes exclusion - participant is receiving placebo run-in or other run-in treatment	Report all	Report if: - drug/vaccine related. (Follow ongoing to outcome)	Within 24 hours of learning of event
Pregnancy/ Lactation Exposure	Report if: - participant has been exposed to any protocol-specified intervention (eg, procedure, washout or run-in treatment including placebo run-in).  Exception: A positive pregnancy test at the time of the initial screening is not a reportable event.	Report all	Previously reported – Follow to completion/termination; report outcome	Within 24 hours of learning of event
ECI (require regulatory reporting)	Report if: - due to intervention - causes exclusion	Report - Potential DILI - Require regulatory reporting	Not required	Within 24 hours of learning of event
ECI (do not require regulatory reporting)	Report if: - due to intervention - causes exclusion	Report - non-DILI ECIs and those not requiring regulatory reporting	Not required	Within 5 calendar days of learning of event
Cancer	Report if: - due to intervention - causes exclusion	Report all	Not required	Within 5 calendar days of learning of event (unless serious)
Overdose	Report if: - receiving placebo run-in or other run-in medication	Report all	Not required	Within 5 calendar days of learning of event

DILI=drug-induced liver injury; ECI=event of clinical interest; NSAE=nonserious adverse event; SAE=serious adverse event

#### **8.4.2     Method of Detecting AEs, SAEs, and Other Reportable Safety Events**

Care will be taken not to introduce bias when detecting AEs and/or SAEs and other reportable safety events. Open-ended and nonleading verbal questioning of the participant is the preferred method to inquire about AE occurrence.

#### **8.4.3     Follow-up of AE, SAE, and Other Reportable Safety Event Information**

After the initial AE/SAE report, the investigator is required to proactively follow each participant at subsequent visits/contacts. All AEs, SAEs, and other reportable safety events, including pregnancy and exposure during breastfeeding, ECIs, cancer, and overdose will be followed until resolution, stabilization, until the event is otherwise explained, or the participant is lost to follow-up (as defined in Section 7.3). In addition, the investigator will make every attempt to follow all nonserious AEs that occur in randomized participants for outcome. Further information on follow-up procedures is given in Appendix 3.

#### **8.4.4     Regulatory Reporting Requirements for SAE**

Prompt notification (within 24 hours) by the investigator to the Sponsor of SAE is essential so that legal obligations and ethical responsibilities towards the safety of participants and the safety of a study intervention under clinical investigation are met.

The Sponsor has a legal responsibility to notify both the local regulatory authority and other regulatory agencies about the safety of a study intervention under clinical investigation. The Sponsor will comply with country-specific regulatory requirements and global laws and regulations relating to safety reporting to regulatory authorities, IRB/IECs, and investigators.

Investigator safety reports must be prepared for SUSARs according to local regulatory requirements and Sponsor policy and forwarded to investigators as necessary.

An investigator who receives an investigator safety report describing an SAE or other specific safety information (eg, summary or listing of SAE) from the Sponsor will file it along with the IB and will notify the IRB/IEC, if appropriate according to local requirements.

#### **8.4.5     Pregnancy and Exposure During Breastfeeding**

Although pregnancy and infant exposure during breastfeeding are not considered AEs, any pregnancy or infant exposure during breastfeeding in a participant (spontaneously reported to the investigator or their designee), including the pregnancy of a male participant's female partner, that occurs during the study are reportable to the Sponsor as described in Section 8.4.1.

All reported pregnancies must be followed to the completion/termination of the pregnancy.

Any pregnancy complication will be reported as an AE or SAE.

The medical reason (example: maternal health or fetal disease) for an elective termination of a pregnancy will be reported as an AE or SAE. Prenatal testing showing fetus will be born with severe abnormalities/congenital anomalies that lead to an elective termination of a pregnancy will be reported as an SAE for the fetus.

Pregnancy outcomes of ectopic pregnancy, spontaneous abortion, missed abortion, benign hydatidiform mole, blighted ovum, fetal death, intrauterine death, miscarriage, and stillbirth must be reported as serious events (Important Medical Events). If the pregnancy continues to term, the outcome (health of infant) must also be reported.

#### **8.4.6 Disease-related Events and/or Disease-related Outcomes Not Qualifying as AEs or SAEs**

Certain efficacy endpoints, including hospitalizations and mortality, must be collected throughout the study (ie, during both treatment and follow-up). From the time of randomization through 14 days following cessation of study intervention, these events must be reported as described in Section 8.4.1. New Hospitalizations and/or deaths that occur after 14 days following cessation of treatment must continue to be assessed for seriousness and causality. However, they must only be reported to the Sponsor within 24 hours as new SAEs if there is evidence to suggest a causal relationship between the study intervention and the SAE.

#### **8.4.7 Events of Clinical Interest**

Selected serious and nonserious AEs are also known as ECIs and must be reported to the Sponsor.

Events of clinical interest for this study include:

1. An elevated AST or ALT lab value that is greater than or equal to 3X the upper limit of normal and an elevated total bilirubin lab value that is greater than or equal to 2X the upper limit of normal and, at the same time, an alkaline phosphatase lab value that is less than 2X the upper limit of normal, as determined by way of protocol-specified laboratory testing or unscheduled laboratory testing.\*

\*Note: These criteria are based upon available regulatory guidance documents. The purpose of the criteria is to specify a threshold of abnormal hepatic tests that may require an additional evaluation for an underlying etiology. The study site guidance for assessment and follow-up of these criteria can be found in the Investigator Study File Binder (or equivalent).

2. Any confirmed (ie, verified by repeat testing) platelet value  $<50,000 / \mu\text{L}$ , as determined by protocol-specified and/or unscheduled laboratory testing.
3. Any confirmed (ie, verified by repeat testing) amylase or lipase value  $>3X$  the upper limit of normal determined by protocol-specified and/or unscheduled laboratory testing.

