#### **4.2.1.2 Safety Endpoints**

Safety evaluations include AE collection, physical examinations (including vital signs) and laboratory tests (hematology and chemistry) performed per the SoA (Section 1.3). AEs will be evaluated and assessed according to the guidelines in Section 8.4 and Appendix 3. Participants may be asked to return for unscheduled visits to perform additional safety monitoring.

In preclinical studies, mild hematologic toxicity was noted on Day 7 which progressed to more severe pancytopenia after 14-21 days of continuous exposure at 2.2-fold and 0.5-fold the NHC exposure at the 200 mg Q12H and 800 mg Q12H human dose of MK-4482 respectively. These changes were fully reversible (Section 2.3). There have been no clinically significant abnormalities observed in hematological laboratory tests in the Phase 1 study

(MK-4482-004). However, based on pre-clinical findings, participants in this study will be monitored for any signs of bone marrow toxicity, including monitoring of CBC and platelets after initiating study intervention.

In preclinical studies, elevated liver enzymes were noted in rats at 72-fold the NHC exposure at 800 mg Q12H and not noted in dogs at 22-fold the NHC exposure at 800 mg Q12H. No clinically significant abnormalities in liver parameters were noted in the Phase 1 study at any dose. However, elevated LFTs with a DILI pattern will be considered an ECI and closely monitored.

No test-article related pathology changes in the pancreas to indicate pancreatic toxicity were noted in nonclinical studies, and lipase and amylase were not measured. Transient elevations of serum lipase were observed at least 3 days after last dose in the Phase 1 study. The occurrence and magnitude of these elevations did not appear to be dose related, and they were not associated with abdominal/gastrointestinal symptoms. However, as asymptomatic lipase elevations and clinical pancreatitis have been associated with some nucleoside analogs, changes in amylase/lipase will be considered an ECI and closely monitored.

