## 9.6.2 Statistical Methods for Safety Analyses

Safety and tolerability will be assessed by clinical review of all relevant parameters including AEs, laboratory values and vital signs.

The analysis of safety results will follow a tiered approach as shown in [Table 6](#). The tiers differ with respect to the analyses that will be performed. For this protocol, only ECIs are considered Tier 1 events. Adverse events (specific terms as well as system organ class terms) and events that meet predefined limits of change (PDLCs) in laboratory values or vital signs will be classified as belonging to "Tier 2" or "Tier 3" based on the number of events observed.

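### The amylase/lipase ECI counts only after a verifying repeat test with no set window, so a transient post-treatment rise may reach no between-group comparison

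*Combined protocol and SAP*

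**What the plan says.** Section 8.4.7 lists three ECIs. The liver criterion has no confirmation condition. The other two begin "Any confirmed (ie, verified by repeat testing) platelet value" and "Any confirmed (ie, verified by repeat testing) amylase or lipase value". The amylase/lipase threshold is more than 3 times ULN, "determined by protocol-specified and/or unscheduled laboratory testing".

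Section 4.2.1.2 gives the background: "Transient elevations of serum lipase were observed at least 3 days after last dose in the Phase 1 study". It adds that the rises did not appear dose related and came without abdominal or gastrointestinal symptoms. Because some nucleoside analogs have been linked to lipase elevations and pancreatitis, it says that "changes in amylase/lipase will be considered an ECI and closely monitored". No confirmation condition appears there.

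Section 8.3.4 holds the repeat instruction. Its trigger is a result regarded as clinically significant, either while the participant is on study or in the two weeks after dosing ends. For such results, "every attempt should be made to perform repeat assessments until the values return to normal or baseline"; a newly established baseline also ends the obligation. Clinical significance is the investigator's judgement, and no time limit is set for the first repeat.

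Section 9.6.2 states: "For this protocol, only ECIs are considered Tier 1 events". Under Table 6 they alone receive a p-value, by the unstratified Miettinen and Nurminen method.

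**The concern.** Whether a threshold crossing becomes a Tier 1 event depends on whether and when a site repeats the test, and the plan fixes neither. For a lasting abnormality this matters little, because the next scheduled draw will confirm it. For a short rise after treatment, which is the pattern reported for lipase in Phase 1, a late repeat may already be back in range. The crossing would then not be a Tier 1 event.

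That would be tolerable if another planned analysis counted single values over the same period. The natural candidate, the predefined limits of change (PDLC) in Section 9.4.2, stops when treatment stops. At stake is a between-group count of post-treatment amylase/lipase crossings, which the plan as written may not produce although the data are collected.

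**Working it through.** **1. When a post-treatment rise would be sampled.** Inputs: Section 8.1.8.1 places the last of ten doses on Day 5 to 7. The Schedule of Activities (1.3) has central chemistry at Day 1, Day 3, EOT, Day 10 (±1, so Day 9–11), Day 15 (+3, so Day 15–18) and Day 29 (+3, so Day 29–32), with no dedicated confirmatory draw.

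- Last dose to Day 10 draw: 9 − 7 = 2 to 11 − 5 = 6 days.
- Last dose to Day 15 draw: 15 − 7 = 8 to 18 − 5 = 13 days.
- Day 10 draw to Day 15 draw: 15 − 11 = 4 to 18 − 9 = 9 days.
- Day 15 draw to Day 29 draw: 29 − 18 = 11 to 32 − 15 = 17 days.
- End of the 14-day reporting period (8.4.1, 9.4.2): 5 + 14 = Day 19 to 7 + 14 = Day 21.

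A rise at least 3 days after the last dose would thus first be seen on schedule at Day 10 or later. If first seen at Day 15, no later scheduled draw falls inside the reporting period. Only an unscheduled repeat could confirm it there.

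**2. Where an unrepeated crossing could still be counted.**

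- PDLC (9.4.2): uses the most abnormal single value, but only while on study intervention. Table 6, footnote b, also restricts PDLCs to endpoints not already pre-specified in Tier 1 or Tier 2.
- Continuous summaries (9.6.2): baseline, on-treatment and change from baseline, as summary statistics rather than counts of crossings.
- Adverse events: a laboratory value becomes an AE if the investigator considers it clinically significant (Appendix 3). It reaches Tier 2, with a confidence interval, once at least 4 participants in one group have the event.

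Only the AE route covers the post-treatment window, and it rests on the same judgement that triggers the repeat.

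**3. The plan's safety power.** Table 9 (9.9.3) gives about 90% for 1% vs 4%, 575 per group, two-sided 5%. With pooled rate 0.025:

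- SE under no difference = √(0.025 × 0.975 × 2/575) = 0.00921
- SE under the alternative = √((0.01 × 0.99 + 0.04 × 0.96)/575) = 0.00917
- Power = Φ((0.03 − 1.96 × 0.00921)/0.00917) = Φ(1.30) = 90.4%

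The plan's figure is reproduced. Exact enumeration of the score test gives 92.9%. Both treat every occurrence as counted.

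**4. Illustration only.** The documents give no confirmed fraction, so f is an assumption. Multiplying both rates by f, the exact score test gives:

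| f | counted rates | power |
|---|---|---|
| 1.00 | 1.00% vs 4.00% | 92.9% |
| 0.75 | 0.75% vs 3.00% | 83.8% |
| 0.50 | 0.50% vs 2.00% | 64.4% |
| 0.25 | 0.25% vs 1.00% | 35.2% |

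The opposite error has a price too. If counting single values adds spurious crossings equally to both arms (also an assumption), the same test gives:

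| added per arm | rates | power |
|---|---|---|
| 0.2 points | 1.2% vs 4.2% | 90.4% |
| 0.5 points | 1.5% vs 4.5% | 86.7% |
| 1.0 point | 2.0% vs 5.0% | 80.6% |

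The documents fix neither input, so they do not show which definition is the more powerful.

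**The case against.** The strongest reply is that repeat testing is provided for. Section 8.3.4 tells sites to make every attempt. Unscheduled results count towards the ECI, unscheduled visits and extra tests are allowed, and the serial chemistry draws can themselves confirm. A value above a protocol-defined ECI threshold is one that an attentive investigator would probably repeat. Clinically significant values also become AEs, and no safety decision rule turns on the Tier 1 p-value. Confirmation has a purpose as well, since it screens out spurious single results.

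Much of this stands, and it rules out several stronger readings that a reader might infer:

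- That repeats are absent. They are discretionary and without a deadline, which is a smaller gap.
- That platelets share the problem. Transience is reported for lipase only. The dog haematology changes in Section 4.3.1 were reversible but grew more severe from Day 14 under continued dosing, which does not suggest a value that is gone before a repeat.
- That Phase 1 showed a drug effect above the ECI threshold. The documents report neither values above 3 times ULN nor how long the rises lasted, and they report no apparent dose relation.
- That the Tier 1 test is biased. Non-confirmation that is equal in blinded arms costs sensitivity and leaves the type I error and risk ratio intact.
- That power falls to a particular figure. Table 9's rates are hypothetical, and the confirmed fraction is assumed.

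The reply does not supply a count of single post-treatment values. The repeat and the AE route both depend on investigator judgement, and an asymptomatic rise may not be judged significant.

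**Conclusion.** The concern holds for amylase and lipase, as a gap in the analysis that is cheap to close. The confirmed ECI is less sensitive to a transient rise after treatment than a single-value count would be, and the on-treatment analyses do not cover that period. An unrepeated crossing may therefore appear in no between-group comparison unless it is reported as an AE. Sections 4.2.1.2 and 8.4.7 also describe the ECI differently, one with the confirmation condition and one without.

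The size of the loss cannot be computed from the documents. The conclusion rests on the sampling intervals, on the Phase 1 description of lipase rises as transient and post-dose, and on the possibility that some such rises exceed 3 times ULN and are not repeated in time. Replacing the confirmed event as the Tier 1 endpoint is not justified, because the noise added by single values is equally unknown.

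**What to change.** In Section 9.6.2 and Table 6, keep the confirmed ECI as the Tier 1 event. Beside it, add a Miettinen and Nurminen comparison of participants with any single post-baseline amylase or lipase value above 3 times ULN, scheduled or unscheduled, through 14 days after the last dose. State how many crossings in each arm were never repeated. The same row may be shown for platelets for completeness, without claiming transience there.

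Reconcile Section 4.2.1.2 with Section 8.4.7 on whether confirmation is part of the ECI. ECI reporting and the Section 7.1 discontinuation wording need no change for this purpose.

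The cost is SAP wording and one or two table rows from data already collected. The drawback is that some spurious single values will be counted in both blinded arms, which is why the two counts should be shown side by side.
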